Clinical Study Protocol	
Drug Substance	Selumetinib
Study Code	D1346C00011
Version	3.0
Date	30 Sep 2021

A Phase 1 Open Label Study to Assess the Safety, Tolerability, Pharmacokinetics and Clinical Efficacy of Selumetinib, a Selective Mitogen Activated Protein Kinase Kinase (MEK) 1 Inhibitor, in Chinese Paediatric and Adult Subjects with Neurofibromatosis Type 1 (NF1) and Inoperable Plexiform Neurofibromas (PN)

Sponsor: AstraZeneca AB, [name].

Regulatory Agency Identifying Number(s): NCT number: NCT04590235

DOCUMENT HISTORY	
Document	Date
Amendment 2	30 September 2021
Amendment 1	02 March 2020
Initial creation	12 August 2019

DOCUMENT HISTORY

Amendment 2 (30 September 2021)

Overall Rationale for the Amendment:

The primary rationale for this amendment is to revise the DCO timepoints and add study mitigation language which will provide sites with measures that may be implemented if a participant is not able to visit a study site to ensure that the clinical trial can continue whilst minimizing risk to the participant, maintaining compliance with GCP, and minimizing risks to the study integrity. Additional changes incorporated are described in the below. Minor clarifications/changes are also incorporated in the body of the Clinical Study Protocol(CSP) that are not mentioned in the table below.

Section # and Name	Description of Change	Brief Rationale	Substantial/Non- substantial
1.2 Synopsis4.4 End of study definition9.5 Statistical analyses9.6 Interim analyses	Revise DCO timepoints	Primary and final DCO timepoints are revised based on results from global SPRINT study, and the new primary and final DCO timepoints would provide sufficient data to evaluate safety, efficacy of selumetinib in Chinese subjects with NF1 and inoperable PN. An interim analysis is added to assess PK, safety, tolerability and efficacy data.Also, end of study time is updated according to the new final analysis DCO.	Substantial
 6.1.1 Investigational products, Table 4 Dosing nomogram for the selumetinib PK study 6.6 Dose modification and discontinuation, Table 7 	Revised the recommended dosage for BSA 0.55-0.69 m ²	The protocol has been aligned to the updated Global dose recommendation guidelines for Selumetinib that patients with BSA 0.55 to 0.69 m ² should be given 20 mg in the	Substantial

Section # and Name	Description of Change	Brief Rationale	Substantial/Non- substantial
Two-step Dose Modification Procedure		morning and 10 mg in the evening. The recommended dose reductions for this BSA	
Recommended Dosage of Selumetinib for Co- administration with Strong or Moderate CYP3A4 or CYP2C19 Inhibitors		bracket have also been updated in line with the Global dose reduction recommendation guidelines for Selumetinib.	
 4.1.1 Study conduct mitigation during study disruptions due to cases of civil crisis, natural disaster, or public health crisis Appendix J 	Added guidance on study continuity in event of public health or civic crisis	This section details the measures that may be implemented if a participant is not able to visit a study site whilst minimizing risk to the participant, maintaining compliance with GCP, and minimizing risks to study integrity. These changes will only be initiated at a time of study disruption.	Substantial
8.3.11 Adverse events of special interest	Update Table 11 to follow latest project specific safety requirements from global safety for reorganizing AESI	Follow global streamlined AESI list which was organized based on the understanding of the safety profile in adult patients with advanced cancer and paediatric patients with NF1 related symptomatic inoperable PN combined with the safety knowledge gained from global submission activities, and to focus on significant medical/clinical concepts.	Substantial
Table 1: Scheduled of assessments	Remove the visit window of C1D8	Subjects need to hospitalized for intensive PK collection. Removal of visit window will minimize the operation burden and ensure the PK collection smoothly.	Non-Substantial
1.2 Synopsis2.1 Study rationale	Revise wordings for the study objectives for	Wordings describing study objectives are revised to	Non-substantial

Section # and Name	Description of Change	Brief Rationale	Substantial/Non- substantial
	paediatric and adult cohorts	keep consistent with Table. 2 study objectives.	
Appendix H Table 33	The drug-drug interactions guidance are updated to recommended dose reductions if a strong or moderate CYP3A4 or CYP2C19 inhibitor must be co-administered with selumetinib. Remove CYP2C19 column in Table 33	The protocol has been aligned to the updated Global recommendation guidelines for Selumetinib. CYP2C19 has a smaller contribution to selumetinib metabolism, compared to CYP3A4, and no PKPD relationship has been observed for efficacy therefore CYP2C19 inducers are permitted	Non-substantial

Amendment 1 (2 March 2020)

Overall Rationale for the Amendment:

Section # and Name	Description of Change	Brief Rationale	Substantial/Non- substantial
Table 1; 8.5 Pharmacokinetics: Table 11 & 12	Updated PK sample collection time point	Based on the half-life of selumetinib, adjusted PK timepoint	Non-substantial
1.2 Synopsis & Table 2 - Secondary objective; 9.4.3.1.1 Objective response rate	Clarify confirmed response definition	Clarify how a PR is deemed to be 'confirmed' as per approach in SPRINT Phase II Stratum 1.	Non-substantial
1.2 Synopsis: Treatments and treatments duration	Add reference for BSA calculation formula for paediatric subjects	Based on China local guideline as reference	Non-substantial
 1.2 Synopsis: Treatments and treatments duration; 4.4 End of study definition; 8.5 Pharmacokinetics; 	Interim analysis wording was removed	Preliminary PK analysis wouldn't trigger DBL and DCO, thus it's inappropriate to call it interim. Thus, the wording of "interim" is removed.	Non-substantial

Section # and Name	Description of Change	Brief Rationale	Substantial/Non- substantial
9.5 Statistical analyses;9.6 Interim analyses			
 1.2 Synopsis: Treatments and treatments duration; Figure 1. Study Design; 4.4 End of study definition; 9.5 Statistical analyses 	Revise wording to specify the primary and final DCOs	Clarification of 2 DCOs	Non-substantial
 2.2 Background; 2.3.1 Overall benefit/risk assessment; 4.2 Scientific rationale for study design 	Update Clinical data of SPRINT Phase I and Phase II	Based on SPINT study CSR of Phase I and Phase II stratum I	Non-substantial
4.1 overall design;5.1 inclusion criteria 6	Add definition of PN subtypes and clarify that solitary nodular PN cannot be selected as the target or non-target PN; Clarify that the target PN must be classified as either typical or nodular (ie must not be solitary nodular) Remove lesion measurability and suitability confirmation prior to enrolment	The definition is consistent with SPRINT and confirmed by [name] Clarify that a solitary nodular PN cannot be selected as the target or non-target PN as solitary nodular PN may have different biology and respond differently to treatment. MRI acquisition training will be provided to sites to mitigate the risk of enrolling subjects where baseline MRI is low quality/ target PN not measurable	Non-substantial
4.3 Justification for dose	Updated Clinical data of SPRINT Phase I and Phase II Stratum I	Based on SPRINT study CSR of Phase I and Phase II stratum I	Non-substantial
6.1.1 Investigational products	Update instruction for next dosing if scheduled dose missed	Based on PK characteristics	Non-substantial

Section # and Name	Description of Change	Brief Rationale	Substantial/Non- substantial
6.6 Dose modification and discontinuation	Clarified Dose modification plan	Based on Toxicity Management Guideline	Non-substantial
7.1 Discontinuation of study treatment	Patients who achieved PR and then meet the criteria of PD to be permitted to remain on study treatment as long as their PN remain less than 20% above baseline and receiving clinical benefit	Updated to be consistent with latest SPRINT CSP.	Non-substantial
7.1.3 Procedures for discontinuation of study treatment	Added the wording on tumour assessment follow up schedule	To assess the response of selumetinib on tumour, continued tumour assessment is required in study subjects who discontinued study treatment due to reason other than disease progression	Non-substantial
8.1.1 Tumour response	Provided details for image collection and review process Redefinition on the non- target lesion	Clarification of image collection process REiNS guidance doesn't specify the number of non-target lesions to be followed or the definition of 'unequivocal progression' of a non- target lesion. Based on learnings from SPRINT, one clinically relevant non-target as well as the target PN is sufficient to represent disease burden	Non-substantial
	Clarification on the definition of unequivocal progression	In SPRINT, 'unequivocal progression' of non-target PN required the investigator to assess the lesion as clinically relevant as well as volumetric progression. Therefore, definition of 'unequivocal progression' was updated to reflect practice in SPRINT.	
	Clarification on the confirmed partial response	Clarify how a PR is deemed to be 'confirmed' as per approach in SPRINT Phase II Stratum 1.	

Section # and Name	Description of Change	Brief Rationale	Substantial/Non- substantial
8.1.3.1.1 FLACC pain scale (3 years)	FLACC pain scale training provided to paediatric subjects' parents	Clarification of operational process of FLACC pain scale	Non-substantial
8.1.3.1.2 Faces pain scale - revised (4 to 17 years)	Updated instructions on how to manage subjects who are unable to read	Provide guidance to handle the scenario when subject have difficulties reading the Faces pain scale.	Non-substantial
8.1.3.1.3 NRS-11 (adult cohort only)	Updated the characteristic and number of selected pain	Based on the data of SPRINT phase II stratum I study	Non-substantial
 8.1.3.1.5 Pain medication survey (all subjects); Table 8; Appendix I – Pain Medication survey 	Updated pain medication survey will be collected on paper	Adoption of paper version due to the limitation of free text in electronic COA version	Non-substantial
8.1.3.6 administration of COAs	Added a section on administration of COAs	Provide guidance on how to administer of COAs	Non-substantial
Appendix E Guidance for management of specific adverse events	Added guidance for management of paronychia. Update existing guidance to make it clearer and easy- execution for both adult and paediatric patients.	Updated or New information from global updated Toxicity Management Guidelines (TMG) documents.	Non-substantial
Appendix G Performance status scales	Updated the Performance status scales	Updated scale	Non-substantial

1.1 Schedule of activities

Table 1Schedule of assessments

Visits ^a Activities/ Assessments	Screenin g ^b		C 0		C1		C2	C3	C4	C5 to C12	C13 to C24	C>24 ^c	EoT ^d	30-day Safety Follow-up (Adult and Paediatric) ^e	Long-term Post-treatment safety Follow-up (Paediatric Only) ^f	Details in section
Day of each cycle	-28 to -1	1	2	1	8	28	28	28	28	28	28	28	NA	NA	NA	
Study day	-28 to -1	1	2	3	10	30	58	86	114	142 to 338	366 to 674	>674	NA	EoT + 30 days	Up to EoT + 1 year	
Visit window (days)		0	0	0	0	±7	±7	±7	±7	±7	±7	±7	NA	+7	±7	
Informed consent	X															Section 5.1
Inclusion/exclusion criteria	Х															Sections 5.1 and 5.2
Hospitalisation		X g	X g		Xg											Sections 4.1 and 8.5
Routine clinical proced	ures						1	1								
Demography	Х															Section 5.1
Medical history	Х															Sections 5.1 and 5.2
Hepatitis serology, HBV PCR ^h , HCV PCR ⁱ	X															Section 5.2
Concomitant medications/treatments	•											1	1	1	•	Section 6.5
Routine safety measure	ements														r	

Visits ^a Activities/ Assessments	Screenin g ^b	n (20		C1		C2	C3	C4	C5 to C12	C13 to C24	C>24 ^c	EoT ^d	30-day Safety Follow-up (Adult and Paediatric) ^e	Long-term Post-treatment safety Follow-up (Paediatric Only) ^f	Details in section
Day of each cycle	-28 to -1	1	2	1	8	28	28	28	28	28	28	28	NA	NA	NA	
Study day	-28 to -1	1	2	3	10	30	58	86	114	142 to 338	366 to 674	>674	NA	EoT + 30 days	Up to EoT + 1 year	
Visit window (days)		0	0	0	0	±7	±7	±7	±7	±7	±7	±7	NA	+7	±7	
Clinical chemistry (fasting) ^j	X				X	X	Х	X	X	X	Х	Х	Х	X		Section 8.2.1
Haematology ^j	Х				Х	Х	Х	Х	Х	Х	Х	Х	Х	Х		Section 8.2.1
Urinalysis ^j	Х				Х	Х	Х	Х	Х	Х	Х	Х	Х	Х		Section 8.2.1
Pregnancy test ^k	Х	Х				Х	Х	Х	Х	Х	Х	Х	Х			Section 8.2.1.1
Physical examination ^{j,1}	Х	Х		Х	Х	Х	Х	Х	Х	Х	Х	Х	Х	X		Section 8.2.2
Vital signs ^{j,m}	Х	Х		Х	Х	Х	Х	Х	Х	Х	Х	Х	Х	X		Section 8.2.3
Height and weight ^{j,n}	Х	Х				Х	Х	Х	Х	Х	Х	Х	Х	X	Х	Section 8.2.4
ECG ^{j,o}	Х					Х	Х	Х	Х	Х	Х	Х	Х	X		Section 8.2.5
Echocardiogram ^{j,p}	Х					Х	Х	Х	Х	Х	Х	Х	Х	X		Section 8.2.6
Ophthalmologic examination ^{j,q}	Х					X	Х	Х	X	Х	Х	Х	Х	X		Section 8.2.7
X-Ray (hand and wrist; paediatric cohort) ^r	X															Section 8.2.9
Tanner stages (paediatric cohort) and performance status ⁱ	Х					X	Х	X	Х	X	Х	Х	Х	X	Х	Sections 8.2.8 and 8.2.10
AEs ^s			1	1	1	1	1	1	1	1	1	1		1	>	Section 8.3

Visits' Activities/ Assessments	¹ Screenin g ^b	C	C O		C1		C2	C3	C4	C5 to C12	C13 to C24	C>24 ^c	EoT ^d	30-day Safety Follow-up (Adult and Paediatric) ^e	Long-term Post-treatment safety Follow-up (Paediatric Only) ^f	Details in section
Day of each cycle	-28 to -1	1	2	1	8	28	28	28	28	28	28	28	NA	NA	NA	
Study day	-28 to -1	1	2	3	10	30	58	86	114	142 to 338	366 to 674	>674	NA	EoT + 30 days	Up to EoT + 1 year	
Visit window (days)		0	0	0	0	±7	±7	±7	±7	±7	±7	±7	NA	+7	±7	
Efficacy measurements	5															
Tumour assessments ^t	X								Х	X	Х	Х	Х			Section 8.1.1
Disfigurement ^u	X									X	Х					Section 8.1.2
Clinical outcome assess	sments															
FLACC pain scale (3 years only) ^v		Х				X	Х	X	X	X	X	Х	Х			Section 8.1.3.1.1
Faces pain scale - revised (4 to 17 years only) ^v		Х				Х	Х	Х	X	X	X	Х	Х			Section 8.1.3.1.2
NRS-11 (adult cohort) ^v		Х				X	Х	Х	Х	Х	Х	Х	Х			Section 8.1.3.1.3
PII ^{v,w}		Х				Х	Х	Х	X	Х	Х	Х	Х			Section 8.1.3.1.4
Pain medication survey ^v		Х				X	Х	Х	X	Х	Х	Х	Х			Section 8.1.3.1.5
PedsQL (paediatric cohort) ^{v,x}		Х				X	Х	Х	X	Х	Х	Х	Х			Section 8.1.3.2.1
EORTC QLQ-C30 (adult cohort) ^v		Х				Х	Х	X	X	Х	X	Х	Х			Section 8.1.3.2.2

CONFIDENTIAL AND PROPRIETARY

Visits ^a Activities Assessments	Screenin g ^b	C	0		C1		C2	C3	C4	C5 to C12	C13 to C24	C>24 ^c	EoT ^d	30-day Safety Follow-up (Adult and Paediatric) ^e	Long-term Post-treatment safety Follow-up (Paediatric Only) ^f	Details in section
Day of each cycle	-28 to -1	1	2	1	8	28	28	28	28	28	28	28	NA	NA	NA	
Study day	-28 to -1	1	2	3	10	30	58	86	114	142 to 338	366 to 674	>674	NA	EoT + 30 days	Up to EoT + 1 year	
Visit window (days)		0	0	0	0	±7	±7	±7	±7	±7	±7	±7	NA	+7	±7	
PlexiQoL (adult cohort) ^v		Х				X	Х	Х	X	Х	Х	Х	Х			Section 8.1.3.2.2
Physical functioning (PROMIS) ^{v,y}		Х				X	Х	Х	X	Х	Х	Х	Х			Section 8.1.3.3
PGIS ^{v,z}		Х				Х	Х	X	Х	X	Х	Х	Х			Section 8.1.3.4
PGIC ^{v,z}						Х	Х	Х	Х	Х	Х	Х	Х			Section 8.1.3.5
Pharmacokinetic measu	rements															
PK blood samples ^g		X	Х		Х											Section 8.5
Study treatment admini	istration									·						
Dispense/return of selumetinib ^{aa}		X		Х		X	Х	X	X	X	X	Х				Section 6
Study treatment compliance ^{bb}		Х		Х		X	Х	Х	X	X	Х	Х				Section 6.4

AE=adverse event; anti-HBc=hepatitis B core antibody; BP=blood pressure; C=cycle; DNA=deoxyribonucleic acid; ECG=electrocardiogram; EORTC QLQ-C30=European Organisation for Research and Treatment of Cancer Quality of Life Questionnaire Core 30; EoT=end of treatment; FLACC=Face, Legs, Activity, Cry, Consolability; HBsAg=hepatitis B surface antigen; HBV=hepatitis B virus; HCV=hepatitis C virus; NA=not applicable; NRS=Numeric Rating Scale; PCR=polymerase chain reaction; PedsQL=Paediatric Quality of Life Inventory; PGIC=patient's global impression of change; PGIS=patient's global impression of severity; PII=Pain Interference Index; PK=pharmacokinetics; PlexiQoL=plexiform neurofibromas quality of life scale; PROMIS=Patient-Reported Outcomes Measurement Information System; RNA=ribonucleic acid.

^a Assessments will be performed at the end of each cycle. Selumetinib will be dispensed after all assessments have been performed and the next cycle will begin at that point.

- ^b Screening tests should be performed within 28 days before the first administration of study treatment, unless otherwise indicated.
- ^c Treatment with selumetinib may be continued until disease progression or unacceptable drug-related toxicity, whichever occurs first.
- ^d The EoT visit will be performed for subjects who permanently discontinue study treatment for any reason (except for death, lost to follow-up or withdrawal of consent).
- ^e The 30-day safety follow-up assessments will be conducted at 30 days post-last dose/EoT for both paediatric and adult cohorts.
- ^f Long-term post-treatment safety follow-up assessments will be conducted for 1 year (at 6 and 12 months post-treatment) for paediatric subjects only.
- ^g Subjects need to be hospitalised for intensive PK sampling during the single dose period (from Cycle 0 Day -1 to Cycle 0 Day 2) and on Cycle 1 Day 8. During Cycle 0, PK samples will be collected pre-dose, 30 minutes, and 1, 1.5, 3, 6, 8, 12, 24 and 30 hours post-dose. At Cycle 1 Day 8, PK sample time points will be collected pre-dose, 30 minutes, and 1.5, 3, 6, and 12 hours post-dose.
- ^h Subjects who are anti-HBc positive and who are HBsAg negative will need to have a negative HBV DNA PCR result before enrolment.
- ⁱ Subjects who are hepatitis C antibody positive will need to have a negative HCV RNA PCR result before enrolment.
- ^j Assessments will be performed at screening and at the end of each cycle up to the end of Cycle 4, every 2 cycles up to the end of Cycle 12, every 4 cycles up to the end of Cycle 24, and every 6 cycles thereafter, as long as the subject remains on study treatment. Assessments may also be performed at other visits during Cycles 0 and 1, as detailed. Screening assessments are suggested to be performed as close to Cycle 0 Day 1 and within 14 days.
- ^k Pregnancy testing will be performed at screening, Cycle 0 Day 1 and at the end of each cycle in women of childbearing potential only (see Section 5.1) and more frequently, if clinically indicated. A urine or serum pregnancy test is acceptable. Screening assessments are suggested to be performed as close to Cycle 0 Day 1 and within 14 days.
- ¹ The complete physical examination includes an assessment of the following: general appearance, respiratory, cardiovascular, abdomen, skin, head and neck (including ears, eyes, nose and throat), lymph nodes, thyroid, musculoskeletal (including spine and extremities) and neurological systems.
- ^m Axillary temperature, pulse rate, oxygen saturation by pulse oximetry, respiratory rate, and BP will be assessed. Assessments of BP and pulse rate should be assessed in a sitting position and preceded by at least 5 minutes of rest in a quiet setting without distractions (e.g. television, cell phones). Manual techniques will be used only if automated devices are not available.
- ⁿ Height and weight measurements will be performed in light clothing and with shoes off.
- ^o Subjects should be supine and at rest 5 minutes prior to recording the ECG.
- ^p The subject should be examined using the same machine and operator throughout the study wherever possible.
- ^q Ophthalmologic assessments may be performed more often, if clinically indicated.
- ^r An x-ray will be performed at screening and at other visits/cycles, if clinically indicated.
- ^s AEs will be collected from the time of signing the informed consent form, throughout the treatment period, and including the follow-up period.
- ^t Tumour assessments will be performed at screening and every 4 cycles (16±1 weeks) up to the end of Cycle 24 (i.e. at the end of Cycles 4, 8, 12, 16, 20, and 24). From the end of Cycle 24, tumour assessments will be performed every 6 cycles (24±1 weeks) as long as the subject remains on study treatment or until disease progression. Subjects who discontinue study treatment due to reasons other than disease progression will continue to undergo tumour assessments for approximately 1 year, if clinically applicable, and the assessment schedule should continue per the regular tumour assessment interval.
- ^u Disfigurement assessments will be performed at screening and at the end of Cycles 8, 16 and 24 as long as the subject remains on study treatment.
- ^v Baseline clinical outcome assessments should be performed prior to and as close to the first dose of selumetinib as possible (PGIC should not have any baseline assessments). Post-baseline assessments should be performed at the end of each cycle up to the end of Cycle 4, every 2 cycles up to the end of Cycle 12, every 4 cycles up to the end of Cycle 24, and every 6 cycles thereafter, as long as the subject remains on study treatment. In the pediatric cohort, the pain medication survey will be completed on paper by the parent. In the adult cohort, the pain medication survey will be completed on paper by the patients. Other assessments will be performed electronically using on-site tablets.

- * Adults and children from 8 to 17 years of age will complete self-reported PII; parents/legal guardian of children from 5 to 17 years of age will complete the parent proxy PII.
- Subject-reported versions are for subjects aged 5 to 7 years, 8 to 12 years, and 13 to 17 years. In addition, the corresponding parent-reported versions will also be included. For subjects 3 to 4 years of age, only the parent-reported version will be included.
- ^y Self-reported short forms will be administered to children from 8 to 17 years of age and parallel parent proxy forms to children aged from 5 to 17 years. In the adult cohort, a newly developed PROMIS short form physical functioning scale will be used.
- ^z Will be parent-reported for children aged up to 17 years and self-reported for children aged 8 to 17 years and adults.
- ^{aa} Following screening, all eligible subjects will first receive a single oral dose of selumetinib 25 mg/m² (Cycle 0). After a period of 2 days, oral selumetinib 25 mg/m² twice daily (approximately every 12 hours) will be administered continuously for 28-day cycles (starting at Cycle 1) with no rest periods between cycles. Selumetinib will be dispensed after all assessments have been performed and the next 28-day cycle will begin at that point. Subjects will therefore be required to attend the site monthly to receive selumetinib. Selumetinib must be taken on an empty stomach (no food or drink other than water for 2 hours before and 1 hour after dosing) with water only.
- ^{bb} Subjects will receive a drug diary to record the specific time each dose was taken and to record reasons for any missed doses.

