Subjects will be administered a single oral dose of selumetinib 25 mg/m² at Cycle 0 Day 1. During the following 2--day washout period, intensive PK samples will be collected before and after this first single dose until pre-dose at Cycle 1 Day 1. From Cycle 1 Day 1, subjects will be administered multiple doses of selumetinib 25 mg/m² twice daily (BID) on a continuous schedule (28 days per cycle). The dose of selumetinib will be capped at 50 mg when body surface area (BSA) is ≥ 1.9 m². Intensive PK samples will be collected on Cycle 1 Day 8 for assessment of the 12-hour PK profile at steady state. Subjects need to be hospitalised for intensive PK sampling during the single dose period (from Cycle 0 Day -1 to Cycle 0 Day 2) and on Cycle 1 Day 8 during the multiple dose period.

Subjects will continue to receive selumetinib until disease progression or unacceptable drugrelated- toxicity, whichever occurs first. Selumetinib will be dispensed after all assessments have been performed and the next 28-day cycle will begin at that point. Subjects will therefore be required to attend the site monthly to receive selumetinib. Subjects will receive a drug diary to record the specific time each dose was taken and to record reasons for any missed doses.

All subjects will be evaluated for safety and efficacy at a regular basis, as defined in Table 1.

Safety assessments (clinical chemistry, haematology, urinalysis, physical examination, vital signs, height and weight, ECG, echocardiogram, ophthalmologic assessment, Tanner stages and performance status) will be performed at screening and at the end of each cycle up to the end of Cycle 4, every 2 cycles up to the end of Cycle 12, every 4 cycles up to the end of Cycle 24, and every 6 cycles thereafter, as long as the subject remains on study treatment. Pregnancy tests will be performed at screening and at the end of each cycle. AEs will be collected from the time of signing the informed consent form (ICF), throughout the treatment

CONFIDENTIAL AND PROPRIETARY 35 of 183

period and including the follow-up period. Safety assessments will also be performed at other visits during Cycles 0 and 1, as detailed in Table 1

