8.5 Pharmacokinetics

A pharmacokinetic evaluation will be performed after the first dose of selumetinib, and at steady state in all consenting adult and paediatric subjects. The PK blood sampling time points are shown in Table 12 (single dose) and Table 13 (multiple doses).

Subjects are to be hospitalised for intensive PK sampling during the single dose period (from Cycle 0 Day -1 to Cycle 0 Day 2) and also on Cycle 1 Day 8.

Table 12

Pharmacokinetic sampling schedule (single dose)

Cycle 0	Day	Pre- dose ^a	30 min ^b	1 hr ^c	1.5 hr ^c	3 hr ^c	6 hr ^c	8 hr ^c	12 hr ^c	24 hr ^c	30 hr ^c
	1	х	х	х	х	х	х	х	х	х	х

hr=hour; min=minute.

^a Within 10 minutes prior to dosing.

^b Time allowance: ± 5 minutes.

^c Time allowance: ± 10 minutes.

Table 13 Pharmacokinetic sampling schedule (multiple dos
--

Cycle 1	Day	Pre-dose ^a	30 min ^b	1.5 hr ^c	3 hr ^c	6 hr ^c	12 hr ^c
	8	X	Х	х	X	X	х

hr=hour; min=minute.

^a Within 10 minutes prior to dosing.

^b Time allowance: ± 5 minutes.

^c Time allowance: ± 10 minutes.

Whole blood samples at each time point will be collected for measurement of the plasma concentration of selumetinib and its metabolite N-desmethyl selumetinib following a single dose (Table 12) and multiple doses (Table 13) as specified in Table 1. PK parameters assessed may include, but are not limited to the following after a single dose:

• AUC.

• Area under the concentration-time curve from zero to 12 hours (AUC₀₋₁₂).

- Area under the concentration-time curve from zero to the last measurable concentration (AUC_{0-t}).
- C_{max}.
- Time to maximum plasma concentration (t_{max})
- Terminal half-life $(t_{1/2})$.

PK parameters assessed may also include, but are not limited to the following after multiple doses:

- Area under the concentration-time curve from zero to 12 hours at steady state (AUC_{0-12,ss}).
- Maximum steady-state plasma concentration (C_{max,ss}).
- Accumulation ratio (Rac; AUC and C_{max)}.

Samples will be collected, labelled, stored and shipped as detailed in the Laboratory Manual.

Samples may be collected at additional time points during the study if warranted and agreed upon between the investigator and the sponsor. Instructions for the collection and handling of biological samples will be provided by the sponsor or analytical test site. The actual date and time (24-hour clock time) of each sample will be recorded.

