9.4 Outcome measures for analyses

9.4.1 Calculation or derivation of pharmacokinetic variables

PK analysis of the plasma concentration data for selumetinib and N-desmethyl selumetinib will be performed by AstraZeneca or a Contract Research Organisation on behalf of AstraZeneca. The actual sampling times will be used in the parameter calculations and PK parameters will be derived using standard noncompartmental methods.

Where possible, the following PK parameters will be determined with plasma concentration data of selumetinib and N-desmethyl selumetinib: AUC, AUC₀₋₁₂, AUC_{0-t}, C_{max} , t_{max} , and $t_{1/2}$ after a single dose, and AUC_{0-12,ss}, $C_{max,ss}$, and Rac (for AUC and C_{max}) after multiple doses.

The C_{max} , $C_{max,ss}$ and t_{max} will be determined by inspection of the concentration-time profiles. The $t_{1/2}$ will be calculated as $ln2/\lambda z$, where λz will be calculated by log-linear regression of the terminal portion of the concentration-time profiles where there are sufficient data. The AUC₀₋₁₂, AUC_{0-12,ss}, and AUC_{0-t} will be calculated using the linear/log trapezoidal rule (i.e. "linear-up-log-down": the linear trapezoidal rule is used any time that the concentration data are increasing, and the logarithmic trapezoidal rule is used any time that the concentration data are decreasing). Where appropriate, the AUC_{0-t} will be extrapolated to infinity using λz to obtain AUC. The Rac (AUC) and Rac (C_{max}) will be calculated as the ratio of the AUC_{0-12,ss} or $C_{max,ss}$ following multiple dosing by the AUC₀₋₁₂ or C_{max} following the first dose, respectively.

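### Rac(Cmax) sets a Day 8 peak read without a 1 h sample against a Cycle 0 peak read with one, so it can only equal or fall below the matched-time ratio

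*Protocol*

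**What the plan says.** Table 1, footnote g, gives the single-dose schedule: "During Cycle 0, PK samples will be collected pre-dose, 30 minutes, and 1, 1.5, 3, 6, 8, 12, 24 and 30 hours post-dose". For steady state it gives: "At Cycle 1 Day 8, PK sample time points will be collected pre-dose, 30 minutes, and 1.5, 3, 6, and 12 hours post-dose". Tables 12 and 13 in Section 8.5 agree. Section 4.1 states the purpose of the second profile: "Intensive PK samples will be collected on Cycle 1 Day 8 for assessment of the 12-hour PK profile at steady state".

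Section 9.4.1 says that Cmax, Cmax,ss and tmax "will be determined by inspection of the concentration-time profiles". It forms the two accumulation ratios by dividing the AUC0-12,ss or Cmax,ss "following multiple dosing by the AUC₀₋₁₂ or C_{max} following the first dose, respectively". The partial AUCs "will be calculated using the linear/log trapezoidal rule". Rac is listed among the parameters of the primary PK objective (Section 3, Table 2).

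The protocol does not restrict either ratio to times sampled on both days, and it gives no reason for leaving out the 1 h sample on Day 8.

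**The concern.** An observed Cmax depends on when blood is drawn. If the denominator may come from a time that the numerator never had, the ratio reflects the sampling schedule as well as accumulation. The error has one direction, so adding subjects does not average it out. Rac(Cmax) could then read a few percent low, in a trial whose purpose is to describe the PK of a Chinese population.

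**Working it through.** **Direction (document only).** The post-dose times are:

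- Cycle 0, within 12 h: F = {0.5, 1, 1.5, 3, 6, 8, 12} h, 7 times.
- Cycle 1 Day 8: S = {0.5, 1.5, 3, 6, 12} h, 5 times, all contained in F.

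Let C0 be the first-dose concentration and Css the Day 8 concentration. The 24 h and 30 h samples and the pre-dose samples are left out because they will not hold the peak.

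- Planned: Rac(Cmax) = max over S of Css ÷ max over F of C0.
- Common times: Rac(Cmax) = max over S of Css ÷ max over S of C0.
- Planned ÷ common = max over S of C0 ÷ max over F of C0 ≤ 1.

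Equality holds when the Cycle 0 peak is at a shared time. The ratio is below 1 only when the Cycle 0 peak is at 1 h or 8 h. An 8 h peak after one oral dose would be exceptional, so the 1 h sample is what matters. The last expression uses Cycle 0 data only, so the sponsor can compute the distortion exactly for each subject.

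**Size (assumptions needed).** The protocol states no tmax, absorption rate, half-life or Rac, so there is no planned figure to reproduce. Simulations assumed first-order absorption with a lag, 12-hourly dosing to steady state, terminal half-life of 5 or 8 h, and one-compartment (flat peak) or two-compartment (sharp peak) disposition. Absorption varied by 40% between subjects and 30% between occasions, with 10% residual error. Selected geometric mean Rac(Cmax) values:

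| Half-life, peak | Typical tmax (h) | Cycle 0 peak at 1 h | True | Planned | Common times | Planned ÷ common |
|---|---|---|---|---|---|---|
| 5 h, sharp | 0.88 | 61% | 1.084 | 0.982 | 1.088 | 0.903 |
| 8 h, sharp | 0.89 | 58% | 1.195 | 1.103 | 1.213 | 0.909 |
| 5 h, flat | 0.82 | 48% | 1.247 | 1.184 | 1.252 | 0.946 |
| 8 h, sharp | 1.48 | 30% | 1.274 | 1.247 | 1.293 | 0.964 |
| 5 h, flat | 1.64 | 24% | 1.263 | 1.238 | 1.269 | 0.976 |
| 5 h, flat | 2.23 | 8% | 1.281 | 1.276 | 1.285 | 0.993 |
| 8 h, flat | 3.32 | 2% | 1.661 | 1.673 | 1.682 | 0.995 |

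For example, 0.982 ÷ 1.088 = 0.903. The loss follows the share of subjects whose Cycle 0 peak is at 1 h. Common times bring the ratio back to within about 2% of the true value in these rows (largest gap 1.213 ÷ 1.195 = 1.015).

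A second set of 12 scenarios (absorption rate 1.5-6 per h, half-life 5-8 h, lag 0.25 h, residual error 10-20%, 1,500 simulated subjects each) gave planned ÷ matched of 0.885 to 0.958, that is 4-12% low.

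In the first row, individual Rac(Cmax) falls below 1 in 56% of subjects as planned, against 32% if both days had the dense schedule.

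**Rac(AUC).** Planned ÷ dense-on-both-days ran from 0.975 to 0.997, so 0.3-2.5% low. In noise-free profiles, removing only the 8 h sample changed Rac(AUC) by less than 1%.

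**The case against.** The strongest reply is that the consequence is small. Rac is one of several descriptive PK parameters. Section 9.1 tests no hypothesis, Section 9.2 bases the sample size on a guideline minimum, and no rule in the protocol uses Rac. All of this stands and keeps the point modest. It does not remove it, because description is what the trial is for and Section 9.4.1 already fixes the formula.

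A second reply is that the schedule can be extended: "Samples may be collected at additional time points during the study if warranted and agreed upon between the investigator and the sponsor". That is optional and by agreement, and does not align the two grids.

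Several stronger readings are tempting and are not supported:

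- *Every subject's ratio is biased.* It is not. The planned and common-time ratios are identical when the Cycle 0 peak is at 0.5, 1.5, 3, 6 or 12 h.
- *Accumulation will be hidden.* Section 9.4.1 also requires Rac(AUC). In the first row of the table, where Rac(Cmax) reads 0.982, Rac(AUC) still reads 1.124 against 1.152 with dense sampling on both days.
- *The missing 8 h sample contributes.* It is immaterial for Cmax and slight for AUC.
- *The unequal morning and evening doses in the smallest BSA band (Table 4) also corrupt Rac.* If both profiles follow the morning dose, the lower evening carry-over belongs to the true accumulation of that regimen. Section 9.5.1 already provides for summaries by dose level.

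**Conclusion.** The point holds for Rac(Cmax). As defined, it is at or below the matched-time ratio in every subject, and strictly below when the Cycle 0 peak is at 1 h. Confidence in the direction is high, since it needs only the two schedules and the formula.

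Confidence in the size is moderate, since it rests on assumed pharmacokinetics. The geometric mean is about 1% low or less if typical tmax exceeds about 2.2 h, about 2-4% low for typical tmax of roughly 1.4-1.9 h, and roughly 3-12% low if peaks cluster near 1 h. Where true peak accumulation is itself only 8-20%, the upper end would remove much of it from this one parameter. Cmax,ss also comes from the sparser grid and may read low for the same reason; a matched ratio does not repair that.

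**What to change.** In Section 9.4.1, calculate Rac(Cmax) from the nominal times common to both days (pre-dose, 0.5, 1.5, 3, 6 and 12 h) and present it next to the ratio of the reported full-grid values. Keep the full Cycle 0 grid for single-dose Cmax and AUC. Leave Rac(AUC) as it is. Add a note that Cmax,ss is read from a grid without 1 h and 8 h samples.

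The cost is a few lines of PK programming and one extra table row, with no additional blood. The downside is that the matched Rac(Cmax) will not equal the quotient of the tabulated Cmax,ss and Cmax. Showing both ratios with a footnote deals with this. Adding a 1 h sample on Day 8 would also align the peaks, but it costs blood and cannot help subjects whose Day 8 profile has already been taken.
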